#### Data Analysis & Statistical Considerations

The approach to analysis will be primarily descriptive. Demographics, questionnaire data, and testing results will be reviewed and summarized using graphical techniques and summary statistics. Where applicable, exact method confidence intervals will be computed around point estimates. Trends over time will be evaluated graphically. The proportion of participants adhering to social distancing guidelines after a positive vs. negative test result will be compared using tests of proportion clustered by participants with various levels of intra-participant correlation. Stratified analyses by test or week number will also be performed. We will explore the associations between positive test results and critical behavioral measures using mixed modeling techniques to account for the participant and household correlations. Analyses will be conducted using SAS (SAS Institute, Cary NC) and R with R Studio (R-project). Point estimates with 95% confidence intervals will be reported. The analysis will be done for applicable study populations as described above, and stratified by participant demographics of

interest (e.g., age, gender). There will be a comparison of the proportion of participants that report adhering to social distancing guidelines after positive vs. negative test result.

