Statistical Analysis Plan*Last Updated: 30 APRIL 2022***EPM (DCRI Only):** 8341 – RADx-UP You and Me COVID Free**NCT05212883****Investigators:**

Duke University: [name], PhD, [name], DPH, [name], FACMI, [name], PhD, MPH, [name]

University of North Carolina-Chapel Hill: [name], MSc; [name], DrPH, MPH

Statisticians: [name]; [name], MS**Faculty Statistician:** [name]**Table of Contents**

Background.....	2
Specific Analysis Aims.....	2
Study Population.....	3
Intervention.....	7
Outcome Variables.....	7
Handling of Missing Data.....	7
Analysis Objectives and Tasks	8
APPENDIX I - Proposed Table and Figure Listing.....	11

Background

The proposed project is a public health intervention with an ecological analysis component. The purpose of this public health intervention, You & Me COVID-Free (YMCF), is to mitigate the community transmission of SARS-CoV-2. This intervention contains two components. One component will be to provide thousands of households in Merced, California the opportunity to test their members frequently at home. The other component will be to promote testing and vaccination awareness and access via community-engaged strategies. CDC, NIH, and academic partners are collaborating on this public health intervention with state and local health departments, as well as community partners, to evaluate the community rollout of frequent at-home testing and the promotion of testing and vaccination awareness and access.

This study will be conducted as a non-randomized ecologic study design to assess the impact of at-home testing interventions and the promotion of vaccination in reducing community transmission in Merced County, CA. We chose Merced County based on several criteria: a) size of the population; b) proportion of Hispanic/Latino/Latinx population; c) established partnerships with the RADx-UP program and the NIH Community Engagement Alliance (CEAL); d) ongoing connection to the local health department; e) county vaccination rates; f) and county Pandemic Vulnerability Index (PVI) score. In this community, 400,000 rapid home tests obtained by the NIH have been distributed in 200,000 kits to community households. Test distribution started on Thursday, November 18, 2021, and the distribution was completed on January 22, 2022.

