A participant could scan a QR code on the participant instruction card or the You & Me COVID-Free bag to access a 1-minute Front Door Survey each time she/he takes a swab test. Individuals will also be invited to complete a more detailed Baseline Survey, which will take about 20 minutes, and then another short follow-up survey (i.e., End of Study Survey) about four weeks later. There is no consent required for each completion of the Front Door Survey and scanning the QR code will start the Front Door Survey automatically. Immediately following the Front Door Survey, the participant is asked if they would like to participate in the sub study. If they agree, they are asked to sign an informed consent form and then given the Baseline Survey to complete. The End of Study Survey is administered 28 days following the completion of the Baseline Survey. The participants who fill out the Baseline Survey and the End of Study Survey will be included in the sub study if they provide a signed and dated informed consent form. There are no exclusion criteria.

As the at-home tests are authorized for children ages 2 and up, these children may also participate in at-home testing, but they will not be enrolled as participants themselves. For children 2 to 14 years of age, an adult must collect the sample and complete the test procedure. Data will be obtained from participants at the individual level.

The Front Door Survey is administered after each swab test by scanning the QR code. There is no consent needed for the Front Door Survey. Immediately following the Front Door Survey, the Baseline Survey is administered at the time of informed consent. The End of Study Survey is administered 28 days following the completion of the Baseline Survey.

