Among 1,208 consented participants in Baseline Survey, no participant completed full set of secondary outcomes, 1,208 participants partially completed secondary outcomes, and no participant were missing all secondary outcomes. See details in Table 2.

Table 2. Missingness of Secondary Outcomes in Baseline Survey

[figure not shown]
	Participant attitudes towards SARS-CoV-2 vaccination		Accessibility to personal protective equipment and distancing in the work place			Self-report COVID-19 testing				Self-report symptoms
	Reasons for getting COVID vaccine	Reasons for not getting COVID vaccine	Have access to necessary facilities to wash	Work require to be in close contact with others	have access to necessary personal protective equipment	Testing method	Have been tested for COVID	Have tested positive for COVID	Accessibility to testing	12 survey items
Missing	0	0	642	643	642	375	216	376	218	275-381
Not missing	1208	1208	566	565	566	833	992	832	990	827-933
Total	1208	1208	1208	1208	1208	1208	1208	1208	1208	1208

Figure 1. Consort Diagram of Front Door Survey and Baseline Survey

Front Door Survey

Baseline Survey

Participants for this sub-study will be recruited within Merced County, California, participating in the larger public health intervention. Recruitment strategies include marketing with public health messaging in collaboration with local health departments, community organizations, media and targeted social media outreach for awareness and education, as well as other strategies that would be tailored to the different distribution scenarios. Participants may be compensated up to \$50 for completion of all surveys. The sample size is up to 300,000 for the sub-study. The test kits distributed as part of the larger study will contain information about the sub-study and how-to consent using either a mobile application (e-consent) accessible free of charge to participants or via phone consenting (verbal consent).

All analyses will be conducted in the evaluable populations corresponding to the Front Door Survey and the Baseline Survey. The Front Door Survey Evaluable Population is defined as entries that have a valid SARS CoV-2 test response (i.e., positive or negative). The Baseline Survey Evaluable Population is defined as participants who were 2 years of age or above at enrollment, consenting to participate in the Baseline and End of Study Surveys.

Intervention

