Test kits consisting of 2 tests per kit were distributed to Merced County households starting on November 18, 2021, through the Merced County Health Department and a coalition of community groups. Outreach and public awareness were done through a multi-pronged education and marketing program including mailers, door hangers, billboards, social media campaigns and targeted ads on local media outlets. Test kit distribution ended on December 31, 2021 and 200,000 test kits were distributed.

Text messages reminders were sent out to all study participants automatically using Twilio, with REDCap as the backend. The messages will include links to complete three surveys, i.e., Front Door Survey, Baseline Survey, and End of Study Survey (28 days later). Participant phone numbers will be provided to Twilio to facilitate the sending of text messages, and Twilio may store metadata about the delivery of the messages, such as successful or failure, and time and date stamps, but no other content will be stored. Messages for this study are one-way only and cannot be replied to.

Outcome Variables

- Primary Outcomes (from Front Door Survey)
 - Participant reasons for test use
 - Participant test result
 - Participant current vaccination status
 - Participant likelihood of future vaccination
 - Participant perspective on easiest way to obtain free oral COVID medicines
- Secondary Outcomes (from Baseline Survey)
 - Participant attitudes towards SARS CoV-2 vaccination
 - Proportion of reasons for getting/not getting a COVID-19 vaccination
 - Participant accessibility to personal protective equipment and distancing in work place
 - Proportion of respondents on access to necessary personal protective and distancing
 - Participant self-report COVID-19 testing and symptoms
 - Proportion of respondents on COVID-19 testing method, testing history and result, accessibility to testing
 - Proportion of respondents who report current symptoms

Handling of Missing Data

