- v) perceived COVID-19 medication access

Analysis: Sociodemographic factors and outcomes will be drawn from the Front Door Survey. For the outcome i) reasons for test use, we will run a logistic regression model on each of the possible choices since participants could choose all that applied. For the outcomes ii) and iii), logistic regression will be used. For the outcome iv) likelihood of future vaccination, ordinal logistic regression will be used. For the outcome v), we will run a logistic regression model on each of the possible answers. Odds ratio estimates and 95% confidence interval will be presented in Table 6.

The methods described above will constitute the main analysis of these primary outcomes. The hypothesis is defined as:

$$H_0: \beta_i = 0$$

$$H_a: \beta_i \neq 0$$

And the logit is the linear function: $\ln(\frac{P}{1-P}) = \alpha + \beta_1 x_1 + \beta_2 x_2 + \dots + \beta_k x_k$

Where β_i is the parameter coefficient of independent variable x_i , and p represents the true probability that the dependent variable $y=1$ (event) given the numeric values on the independent variables. This analysis will be conducted using PROC LOGISTIC in SAS. The hypothesis as expressed above will be tested at a 2-sided significance level of 0.05.

Crucial assumption that must be met for logistic regression is linearity in the logit for continuous independent variables. We will use the Box-Tidwell test and scatter plot to check for linearity between the continuous predictors and the logit. If the linearity assumption is violated, it is necessary to make further adjustments either to the model (including or excluding predictors), or transforming the response and/or predictors. We will use restricted cubic splines to explore non-linear continuous associations.

It is important to note that the independence assumption for the logistic regression models may be violated since a single participant can enter multiple records in the Front Door Survey, but cannot be distinguished. If the violation is occurring then our models are underestimating standard errors, leading to inflated Type I error.

- See Appendix for proposed:
 - o Table 6: Regression estimates for the association between sociodemographic factors and COVID-19 testing, vaccination, and medication outcomes

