Table 6. Regression estimates for the association between sociodemographic factors and COVID-19 testing, vaccination, and medication outcomes

	Reason for test use						Test result		Vaccination status				Perceived easiest place to access COVID-19 oral medications	
	Close contact possible COVID-19 (N= xxx)	Close contact COVID-19 positive (N= xxx)	Household member COVID-19 positive (N= xxx)	Positive COVID-19 test result (N= xxx)		Received at least one vaccine dose (N= xxx)	Likelihood of future vaccination ^a (N= xxx)	Pharmacy only vs. doctor's office or community setting ^b (N= xxx)						
All Respondents ^e (N= xxx)	OR _{Adj} ^c	95% CI	OR _{Adj} ^c	95% CI	OR _{Adj} ^c	95% CI	OR _{Adj} ^c	95% CI	OR _{Adj} ^d	95% CI	OR _{Adj} ^d	95% CI		
Age, years														
<18	X.X	X.X - X.X	X.X	X.X - X.X	X.X	X.X - X.X	X.X	X.X - X.X	X.X	X.X - X.X	X.X	X.X	X.X - X.X	
≥18	
Race														
Black	X.X	X.X - X.X	X.X	X.X - X.X	X.X	X.X - X.X	X.X	X.X - X.X	X.X	X.X - X.X	X.X	X.X	X.X - X.X	
Other	X.X	X.X - X.X	X.X	X.X - X.X	X.X	X.X - X.X	X.X	X.X - X.X	X.X	X.X - X.X	X.X	X.X	X.X - X.X	
Asian	X.X	X.X - X.X	X.X	X.X - X.X	X.X	X.X - X.X	X.X	X.X - X.X	X.X	X.X - X.X	X.X	X.X	X.X - X.X	
Multiple	X.X	X.X - X.X	X.X	X.X - X.X	X.X	X.X - X.X	X.X	X.X - X.X	X.X	X.X - X.X	X.X	X.X	X.X - X.X	
White	
Ethnicity														
Hispanic/Latino/ Spanish	X.X	X.X - X.X	X.X	X.X - X.X	X.X	X.X - X.X	X.X	X.X - X.X	X.X	X.X - X.X	X.X	X.X	X.X - X.X	
Non-Hispanic/Latino/ Spanish	

Language														
English	x.x	x.x - x.x												
Spanish

Note:

NA=odds ratio not estimable due to small sample sizes.

Bolded estimates p<.05.

^aLikelihood of future vaccination per one unit change (Not at all likely to not very likely; Not very likely to somewhat likely; Somewhat likely to very likely).

^bCommunity settings=grocery store, community center, place of worship, community park, neighborhood school, or other.

^cEstimates based on binary logistic regression, adjusted for age, race, and ethnicity.

^dEstimates based ordinal logistic regression, adjusted for age, race, and ethnicity.

^eNumber of All respondents is the number of participants who have complete data on full set of sociodemographic factors (i.e., Age, Race, Ethnicity, and Language), sample size on each outcome could vary based on the number of participants respond to the relevant survey item.

Table 7. Regression estimates for the association between social determinants of health and COVID-19 testing attitude and behavior in Baseline Survey

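### The SAP has no counterpart to the protocol's time trends and fits Objective 5 without a calendar term, so sociodemographic odds ratios for a positive test may be confounded by when groups tested

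*Protocol*

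**What the plan says.** The Protocol, in Data Analysis & Statistical Considerations, makes two statements about time. The first is general and tied to no outcome: "Trends over time will be evaluated graphically". The second comes straight after the comparison of social distancing following positive and negative results: "Stratified analyses by test or week number will also be performed".

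In the SAP, Objective 5 relates age category, race, ethnicity and preferred language to five Front Door Survey outcomes. Reasons for testing get one logistic model per option. For test result and vaccination status, "For the outcomes ii) and iii), logistic regression will be used". Table 6, footnote c, describes the estimates as "binary logistic regression, adjusted for age, race, and ethnicity". No date, week or period appears among the predictors. None of the six objectives contains a time trend or a week stratum. Appendix I is titled as a table and figure listing, but it lists Tables 1 to 7 and no figure.

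On the period covered, the SAP Background says "Test distribution started on Thursday, November 18, 2021, and the distribution was completed on January 22, 2022", while the SAP Intervention section says "Test kit distribution ended on December 31, 2021 and 200,000 test kits were distributed". Entries are made when a test is used: "The Front Door Survey is administered after each swab test by scanning the QR code" (SAP, Study Population). They can therefore arrive after distribution has ended.

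**The concern.** Test result is a primary outcome, and Objective 5 pools every valid entry as if calendar time did not matter. Over several weeks two things can change: the share of tests that are positive, and the mix of people testing. The project aims to reduce community spread, so its own premise is that infection levels can move. Kits went out through the health department and a coalition of community groups, with several kinds of outreach, so it is plausible that groups were reached at different times.

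If both things changed, a group that tested mainly in high-positivity weeks would show a raised odds ratio even if its positivity matched everyone else's in each week. The same could happen for contact-related reasons for testing, because contact with cases is likely to rise when infection is common. Table 6 bolds estimates with p<.05, so a timing effect would be displayed as a demographic difference. The SAP warns about repeat entries by the same person but says nothing about calendar time.

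**Working it through.** **The plan's own figure.** SAP, Handling of Missing Data: 2,510 entries, of which 111 have no valid result. 2,510 − 111 = 2,399, which matches the SAP's evaluable count. This is the most that the test-result model can use, since Table 6 also requires complete sociodemographic data. The documents give no power or effect-size calculation for Objective 5 to reproduce.

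**Length of the rollout.**
- 18 November to 31 December 2021: 43 days, 43/7 = 6.1 weeks.
- 18 November 2021 to 22 January 2022: 65 days, 65/7 = 9.3 weeks.
- The two end dates differ by 65 − 43 = 22 days. Testing may have run longer; no data cut-off date is given.

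**Size of a possible artefact.** The documents give neither positivity by week nor counts of groups by week, so the inputs here are assumptions. Take two periods of equal size, with positivity p1 then p2 in everyone (no group effect within a period). Let a group make up share s1 of entries in the first period and s2 in the second.
- Group positivity: g = (s1·p1 + s2·p2)/(s1 + s2)
- Comparison positivity: c = [(1−s1)·p1 + (1−s2)·p2]/(2 − s1 − s2)
- Pooled OR = [g/(1−g)]/[c/(1−c)]
- SE of log OR = √(sum of the reciprocals of the four expected cell counts), with N = 2,399
- Chance of p<.05, two-sided ≈ Φ(log OR/SE − 1.96) + Φ(−log OR/SE − 1.96)

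Worked case: p 5% then 25%, s 20% then 40%.
- g = (0.01 + 0.10)/0.6 = 0.1833
- c = (0.04 + 0.15)/1.4 = 0.1357
- OR = 0.2245/0.1570 = 1.43
- Group sizes: 0.3 × 2,399 = 719.7, and 1,679.3
- SE = 0.120, log OR = 0.357, z = 2.98, chance of p<.05 = 0.85

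| Positivity, early then late | Group share, early then late | Pooled OR | Chance of p<.05 |
|---|---|---|---|
| constant | any | 1.00 | 5% |
| any | constant | 1.00 | 5% |
| 5%, 15% | 20%, 25% | 1.08 | 8% |
| 5%, 25% | 20%, 25% | 1.12 | 13% |
| 5%, 15% | 20%, 30% | 1.15 | 16% |
| 10%, 30% | 20%, 40% | 1.33 | 76% |
| 5%, 25% | 20%, 40% | 1.43 | 85% |

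The period-adjusted OR is 1.00 in every row, by construction. The rows are a range of what-ifs, not estimates for this study.

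**The case against.** The case on the other side is substantial.

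- **Bias is not shown.** Confounding needs both changing positivity and groups that test at different times. A reader might infer that the odds ratios are confounded; the documents contain no weekly positivity and no group-by-week counts, so they do not support that. The SAP phrase "other strategies that would be tailored to the different distribution scenarios" concerns recruitment and is not evidence on when kits were used. This stands.
- **The week-stratification sentence is not a clear promise for Objective 5.** A reader might infer that the SAP breaks a commitment to stratify these models by week. The sentence follows the social-distancing comparison and names no other outcome. Week number could also mean a participant's follow-up week. The sociodemographic models are an SAP aim that the Protocol does not list. This stands too. The sentence on trends over time is the firmer anchor, because it is general and the SAP has nothing that answers it.
- **Entries may be undated.** No passage says that a Front Door entry carries a test or submission date, and Table 5 lists none. The time stamps in the SAP Intervention section belong to text messages. The End of Study Survey is sent 28 days after the Baseline Survey is completed, so Baseline completion is evidently tracked, but that does not settle the Front Door Survey. The fix therefore needs a fallback.
- **The large figures need large shifts.** The 85% case needs positivity to rise fivefold and a group's share to double. Modest shifts give 8% to 16%. The illustration is also a crude two-group comparison, whereas Table 6 adjusts for other sociodemographic factors.
- **A pooled association is a legitimate description.** The aim is exploratory and the Protocol calls its approach mainly descriptive. A within-week odds ratio answers a somewhat different question. This argues for reporting both, not for leaving time out.

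**Conclusion.** The point holds as a gap with a possible consequence. The Protocol's graphical time trends are missing from the SAP, and Objective 5 pools entries over at least six to nine weeks of distribution with no calendar term. Odds ratios for a positive test, and for contact-related reasons for testing, may therefore be confounded by calendar time, and the planned outputs could neither reveal nor remove it.

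The size is unknown. With no true effect and 2,399 entries, it runs from nothing (OR 1.00, 5% significant), through small (1.08 to 1.15, 8% to 16%), to serious (1.43, 85%). This rests on assumed positivity and shares, two equal periods, a crude comparison, and independent entries, which the SAP itself says may not hold. The conflict between the two distribution end dates is a fact of the text and needs no assumption.

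**What to change.** 1. State in the SAP whether each Front Door entry carries a test or submission date.
2. If it does, add calendar week, or a restricted cubic spline of entry date, to the Objective 5 models for test result and reasons for testing. The SAP already plans such splines for continuous predictors, although Objective 5 lists none. Report the time-adjusted odds ratios beside the pooled ones in Table 6.
3. Add one figure showing, by week, the number of entries, percent positive and group mix. This supplies the Protocol's time trend and shows whether the two conditions for confounding are present.
4. If entries are undated, say that time trends and time adjustment are not possible, and limit the conclusions on sociodemographic differences accordingly.
5. Reconcile 31 December 2021 with 22 January 2022 as the end of distribution.

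The cost is SAP text, one figure and a few parameters. Windows of 6.1 and 9.3 weeks touch at least 7 and 10 calendar weeks, so categorical week needs at least 6 or 9 indicators, and more if entries continued after distribution. A spline needs fewer and is safer where weekly positives are sparse. The main dependency is that entries are dated.

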Statistical Analysis Plan*Last Updated: 30 APRIL 2022***EPM (DCRI Only):** 8341 – RADx-UP You and Me COVID Free**NCT05212883****Investigators:**

Duke University: [name], PhD, [name], DPH, [name], FACMI, [name], PhD, MPH, [name]

University of North Carolina-Chapel Hill: [name], MSc; [name], DrPH, MPH

Statisticians: [name]; [name], MS**Faculty Statistician:** [name]**Table of Contents**

Background.....	2
Specific Analysis Aims.....	2
Study Population.....	3
Intervention.....	7
Outcome Variables.....	7
Handling of Missing Data.....	7
Analysis Objectives and Tasks	8
APPENDIX I - Proposed Table and Figure Listing.....	11

Background

The proposed project is a public health intervention with an ecological analysis component. The purpose of this public health intervention, You & Me COVID-Free (YMCF), is to mitigate the community transmission of SARS-CoV-2. This intervention contains two components. One component will be to provide thousands of households in Merced, California the opportunity to test their members frequently at home. The other component will be to promote testing and vaccination awareness and access via community-engaged strategies. CDC, NIH, and academic partners are collaborating on this public health intervention with state and local health departments, as well as community partners, to evaluate the community rollout of frequent at-home testing and the promotion of testing and vaccination awareness and access.

This study will be conducted as a non-randomized ecologic study design to assess the impact of at-home testing interventions and the promotion of vaccination in reducing community transmission in Merced County, CA. We chose Merced County based on several criteria: a) size of the population; b) proportion of Hispanic/Latino/Latinx population; c) established partnerships with the RADx-UP program and the NIH Community Engagement Alliance (CEAL); d) ongoing connection to the local health department; e) county vaccination rates; f) and county Pandemic Vulnerability Index (PVI) score. In this community, 400,000 rapid home tests obtained by the NIH have been distributed in 200,000 kits to community households. Test distribution started on Thursday, November 18, 2021, and the distribution was completed on January 22, 2022.

This cohort sub-study in a subset of the population will explore human factors in response to testing and vaccination. Participants in the public health intervention who meet eligibility criteria will be invited to participate in the sub-study, consented, and asked to complete questionnaires aimed at evaluating self-reported health conditions, COVID-19 testing and symptoms, social interactions, knowledge of prevention strategies, infection risk, and attitudes towards vaccines. This sub-study will provide participant-level information essential to understand COVID-19 testing and vaccination awareness and access and relevant for implementation of public health interventions in future pandemics.

Further details of the background and the design of the study can be found in the study proposal.

Specific Analysis Aims

1. Characterize self-reported COVID-19 testing and symptoms.
2. Delineate attitudes towards SARS CoV-2 vaccination.
3. Describe infection risk in work place.
4. Explore the relationship between sociodemographic factors, i.e., age, race, ethnicity, and preferred language, and
 - a. reasons for test use,
 - b. test result,
 - c. current vaccination status,
 - d. likelihood of future vaccination,
 - e. perspective on easiest way to obtain free oral COVID medicines.
5. Explore the relationship between social determinants of health, i.e., gender identity, employment, food/water/housing insecurity, health insurance, and COVID-19 challenges, and
 - a. testing attitude (i.e., Participant thinks it is easy to get tested for COVID-19)
 - b. testing behavior (i.e., Participant has been tested for COVID-19)

Study Population

The study population will consist of people who meet the following criteria:

- Adult and child residents who are 2 years of age or greater at enrollment
- Self-report primarily residing within the intervention community (Merced County, California)
- Are participating in the public health intervention, regardless of vaccination status

The questionnaire includes three parts:

- Front Door Survey
- Baseline Survey
- End of Study Survey

A participant could scan a QR code on the participant instruction card or the You & Me COVID-Free bag to access a 1-minute Front Door Survey each time she/he takes a swab test. Individuals will also be invited to complete a more detailed Baseline Survey, which will take about 20 minutes, and then another short follow-up survey (i.e., End of Study Survey) about four weeks later. There is no consent required for each completion of the Front Door Survey and scanning the QR code will start the Front Door Survey automatically. Immediately following the Front Door Survey, the participant is asked if they would like to participate in the sub study. If they agree, they are asked to sign an informed consent form and then given the Baseline Survey to complete. The End of Study Survey is administered 28 days following the completion of the Baseline Survey. The participants who fill out the Baseline Survey and the End of Study Survey will be included in the sub study if they provide a signed and dated informed consent form. There are no exclusion criteria.

As the at-home tests are authorized for children ages 2 and up, these children may also participate in at-home testing, but they will not be enrolled as participants themselves. For children 2 to 14 years of age, an adult must collect the sample and complete the test procedure. Data will be obtained from participants at the individual level.

The Front Door Survey is administered after each swab test by scanning the QR code. There is no consent needed for the Front Door Survey. Immediately following the Front Door Survey, the Baseline Survey is administered at the time of informed consent. The End of Study Survey is administered 28 days following the completion of the Baseline Survey.

The Front Door Survey and the Baseline/End of Study Surveys cannot be linked due to the way they were set up, despite the fact that there are matching record IDs. Each entry in the Front Door Survey corresponds to a unique test result. Multiple test results can correspond to the same participant, but each test result receives a unique record ID so there is no way to link the multiple results to one participant. Each participant can sign up once to take the Baseline Survey and End of Study Survey, and each unique record ID represents one participant in the Baseline and End of Study Surveys. An observation from the Baseline and End of Study Surveys will have the same record ID as an observation in the Front Door Survey. However, this does not necessarily mean that the information across both sets of surveys are from the same participant. In order to clarify the data flow of the YMCF project, the consort diagram in Figure 1 presents data from the Front Door Survey on the number of total entries, the number of valid test results, and completeness of the primary outcomes. It also presents data from the Baseline Survey on the and number of total participants, the number of consented participants, and completeness on secondary outcomes. The primary outcomes correspond to the Front Door Survey and are:

- Participant reasons for test use
- Test result
- Current vaccination status

- Likelihood of future vaccination
- Perspective on easiest way to obtain free oral COVID medicines

Among 2,399 valid-test-result entries in Front Door Survey, 412 entries completed full set of primary outcomes, 1,987 entries partially completed primary outcomes, and none entry were missing all primary outcomes. See details in Table 1.

Table 1. Missingness of Primary Outcomes in Front Door Survey

	Participant reasons for test use	Test result	Current vaccination status	Likelihood of future vaccination	Perspective on easiest way to obtain free oral COVID medicines
Missing	0	0	4	1987	0
Not missing	2399	2399	2395	412	2399
Total	2399	2399	2399	2399	2399

The secondary outcomes correspond to the Baseline Survey and are:

- Participant attitudes towards SARS-CoV-2 vaccination
- Accessibility to personal protective equipment and distancing in the work place
- Self-report COVID-19 testing and symptoms

[figure not shown]
Among 1,208 consented participants in Baseline Survey, no participant completed full set of secondary outcomes, 1,208 participants partially completed secondary outcomes, and no participant were missing all secondary outcomes. See details in Table 2.

Table 2. Missingness of Secondary Outcomes in Baseline Survey

[figure not shown]
	Participant attitudes towards SARS-CoV-2 vaccination		Accessibility to personal protective equipment and distancing in the work place			Self-report COVID-19 testing				Self-report symptoms
	Reasons for getting COVID vaccine	Reasons for not getting COVID vaccine	Have access to necessary facilities to wash	Work require to be in close contact with others	have access to necessary personal protective equipment	Testing method	Have been tested for COVID	Have tested positive for COVID	Accessibility to testing	12 survey items
Missing	0	0	642	643	642	375	216	376	218	275-381
Not missing	1208	1208	566	565	566	833	992	832	990	827-933
Total	1208	1208	1208	1208	1208	1208	1208	1208	1208	1208

Figure 1. Consort Diagram of Front Door Survey and Baseline Survey

Front Door Survey

Baseline Survey

Participants for this sub-study will be recruited within Merced County, California, participating in the larger public health intervention. Recruitment strategies include marketing with public health messaging in collaboration with local health departments, community organizations, media and targeted social media outreach for awareness and education, as well as other strategies that would be tailored to the different distribution scenarios. Participants may be compensated up to \$50 for completion of all surveys. The sample size is up to 300,000 for the sub-study. The test kits distributed as part of the larger study will contain information about the sub-study and how-to consent using either a mobile application (e-consent) accessible free of charge to participants or via phone consenting (verbal consent).

All analyses will be conducted in the evaluable populations corresponding to the Front Door Survey and the Baseline Survey. The Front Door Survey Evaluable Population is defined as entries that have a valid SARS CoV-2 test response (i.e., positive or negative). The Baseline Survey Evaluable Population is defined as participants who were 2 years of age or above at enrollment, consenting to participate in the Baseline and End of Study Surveys.

Intervention

Test kits consisting of 2 tests per kit were distributed to Merced County households starting on November 18, 2021, through the Merced County Health Department and a coalition of community groups. Outreach and public awareness were done through a multi-pronged education and marketing program including mailers, door hangers, billboards, social media campaigns and targeted ads on local media outlets. Test kit distribution ended on December 31, 2021 and 200,000 test kits were distributed.

Text messages reminders were sent out to all study participants automatically using Twilio, with REDCap as the backend. The messages will include links to complete three surveys, i.e., Front Door Survey, Baseline Survey, and End of Study Survey (28 days later). Participant phone numbers will be provided to Twilio to facilitate the sending of text messages, and Twilio may store metadata about the delivery of the messages, such as successful or failure, and time and date stamps, but no other content will be stored. Messages for this study are one-way only and cannot be replied to.

Outcome Variables

- Primary Outcomes (from Front Door Survey)
 - Participant reasons for test use
 - Participant test result
 - Participant current vaccination status
 - Participant likelihood of future vaccination
 - Participant perspective on easiest way to obtain free oral COVID medicines
- Secondary Outcomes (from Baseline Survey)
 - Participant attitudes towards SARS CoV-2 vaccination
 - Proportion of reasons for getting/not getting a COVID-19 vaccination
 - Participant accessibility to personal protective equipment and distancing in work place
 - Proportion of respondents on access to necessary personal protective and distancing
 - Participant self-report COVID-19 testing and symptoms
 - Proportion of respondents on COVID-19 testing method, testing history and result, accessibility to testing
 - Proportion of respondents who report current symptoms

Handling of Missing Data

No imputation will be performed for missing data. Participants who *do not know* or *prefer not to answer* a question used as an outcome variable will be treated as missing data. Survey entries which do not show a valid (positive or negative) SARS CoV-2 test result (N=111) in the Front Door Survey will not be included in the Front Door Survey Evaluable Population. Out of the 2,510 entries in the Front Door Survey, 425 completed survey items on key primary outcomes. Among the 1,313 respondents who consented to participate Baseline and End of Study Survey, 480 completed survey items on key secondary outcomes.

Analysis Objectives and Tasks

- Objective:** Summarize sociodemographic characteristics and medical history of participants in the Baseline Survey Evaluable Population and summarize sociodemographic and test-relevant characteristics of entries in Front Door Survey Evaluable Population

Analysis: Sociodemographic characteristics and medical history summaries will be presented in Table 1. All the sociodemographic characteristics and medical history variables from the Baseline Survey will be summarized by age category (Adult, Minor, Overall) where Adult is defined as age ≥ 18 years of age. Similarly, sociodemographic and test-relevant characteristics of entries will be presented in Table 5. All variables are categorical and will be summarized as counts and percentages. The denominators for the percentages for each variable in Table 1 are defined as the number of participants in the Baseline Survey Evaluable Population who have non-missing data for the variable. The denominators for the percentages for each variable in Table 5 are defined as the frequency of entries in the Front Door Survey Evaluable Population which have non-missing data for the variable.

- See Appendix for proposed:
 - Table 1: Participant Sociodemographic Characteristics and Medical History in Baseline Survey in Merced County, CA
 - Table 5: Sociodemographic and Test-relevant Characteristics in Front Door Survey Entries in Merced County, CA

- Objective:** Summarize self-reported COVID-19 testing characteristics and symptoms corresponding to the Baseline Survey Evaluable Population

